Blood and CSF Biomarker Assessments (Continued)	an indication for treatment-related effects on blood brain barrier permeability and as a correlate with MRI analyses for any incidence of vasogenic edema or microhemorrhage. CSF and plasma will be assayed for A β (1-42), A β (1-40), t-tau, p-tau, tau:A β (1-42) ratios, NfL, GFAP, UCHL1, and panels of cytokines, chemokines, and other circulating factors to determine any treatment-related effects that might correlate with cognitive and activities of daily living changes.
	Serum Anti-Drug Antibody (ADA) Testing for Anti-GM-CSF Antibody will be assayed from serum collected by venipuncture blood draws at baseline, week 3, week 12, week 18, EOT, and follow-up visits.
	Apolipoprotein E (ApoE) Genetic Status will be determined via blood sample collected at Baseline visit.
Imaging Assessments	Fluorodeoxyglucose F18 (FDG) PET scan will be completed as part of baseline and EOT visit.
	MRIs of the brain will be conducted throughout the study period, including during screening period, week 6 visit, week 12 visit, week 18 visit, EOT visit, and at the follow-up visit.
	Amyloid PET utilizing an approved radiotracer (such as Vizamyl (flutemetamol F ¹⁸)) will be done as confirmation of elevated amyloid, or as an optional sub-study if LP is completed as confirmation. If participant consents, the PET will occur during Screening and at the follow-up visit.
Safety Assessments	Blood work including CBCs with differential and comprehensive metabolic panels (CMPs) will be collected at baseline visit, for the remainder of the treatment period, CBCs with differential twice a week and CMP once a week. At the End of Treatment Visit and follow-up visits, CBC with differential only. CBC will be repeated approximately 2 days and 9 days after last dose.
	Physical exams by study physician or qualified designee will be conducted at screening visit, Baseline, week 12, EOT, and follow-up visits.
	Electrocardiograms (ECGs) will be conducted at screening visit, week 12, and EOT visits.
	MRIs of the brain will be conducted throughout the study period, including during screening (Tier 2), week 6 visit, week 12 visit, week 18 visit, EOT visit, and at the follow-up visit.
	Vital signs and adverse events (AEs) will be monitored weekly.
	C-SSRS assessment of suicidality will be conducted at Screening, Baseline week 12 and EOT visits.

2 Schedule of Events

Schedule of Events - Screening Period	
Visit:	Screening Visit

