kSafety blood draws will include CMP (once per week) and CBC + diff (twice per week). EOT and FU visits will not have a CMP, only one CBC draw will be collected for these visits.

¹The LP (if opted in) and blood draw for end of treatment should be conducted at least 2 days after and within 10 days following the final treatment injection, and both performed on the same day with the LP procedure performed first. PT/INR and platelets must have been performed within 3 months of LP procedure, refer to manual of procedures for LP parameters.

LP/PET sequences based on which is used for study inclusion:

If Choose Lumbar Puncture for Study Inclusion (with OPTIONAL AMYLOID PET SUBSTUDY)

	Screening Tier 3	Screening Tier	Baseline	End of Treatment	Follow-up
	Visit	4 Visit	Visit	Visit	Visit
Lumbar Puncture (Mandatory)	X			X	
FDG PET (Mandatory)			X	X	
Amyloid PET (Optional)		X			X

If Choose Amyloid PET for Study Inclusion (with OPTIONAL LUMBAR PUNCTURE SUBSTUDY)

	Screening Tier 3 Visit	Screening Tier 4 Visit	Baseline Visit	End of Treatment Visit	Follow-up Visit
Amyloid PET (Mandatory)	X				X
FDG PET (Mandatory)			X	X	
Lumbar Puncture (Optional)		X		X	

The blood draw for follow-up visit, FDG PET, and Amyloid PET (if opted in) should be conducted within ± 7 days of anticipated visit.

ⁿThe MRI for follow-up visit is only scheduled for participants who participate in the optional Amyloid PET procedure. If the LP is done as a substudy, not for confirmation of the plasma results $A\beta(42)/A\beta(40)$ ratio, it will not be tested at outside lab as inclusion LP is for confirmatory results.

The Enhanced safety blood draws will consist of a cytokines panel (IL 1 beta, IL 2, IL 6, TNF alpha such as from CHCO Lab 10055) recommended by study immunologist and safety monitor at baseline, week 6, 12, 18 and EOT, and lab (such as CHCO LAB9496) testing characterization of activated, senescent, and exhausted T cells done at visits (Baseline, Week 12 and EOT visits)

PThe CBC w/ diff will be repeated approximately 2 days and 9 days after last participant dose at end of treatment or withdrawal from study.

3 List of Abbreviations

AbbreviationTermAβamyloid beta

A $\beta(1-x)$ amyloid beta (1-x) (i.e., the amyloid beta monomer from amino acid 1 to

x [e.g. 1-42])

ADCC Alzheimer's Disease Core Center
ADRC Alzheimer's Disease Research Center

ADCS-ADL Alzheimer's Disease Cooperative Study – Activities of Daily Living

AChEI acetylcholinesterase inhibitor

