Primary Objective To assess long-term tolerability and safety of sargramostim in individuals with mild-to-moderate Alzheimer's Disease (AD).	Effects of sargramostim on white blood cell mobilization will be determined by CBCs with differential. Comprehensive metabolic panels (CMPs), electrocardiograms (ECGs), serology testing for antidrug antibodies (ADAs), physical exams, and high-resolution MRI scans to identify amyloid-related imaging abnormalities (ARIAs) will be performed, and vital signs and adverse events (AEs) will be
	monitored.
Secondary Objective:	Secondary Endpoint Change in cognition from Baseline to End of Treatment (EOT) visit as
To test the hypothesis that sargramostim treatment, as compared to placebo, slows or halts cognitive decline, or improves cognitive functioning in individuals with mild-to-moderate AD.	measured by: The Mini-Mental State Examination(MMSE)
Exploratory Objectives	Exploratory Endpoints
To assess the effect of sargramostim treatment, as compared to placebo, on clinical progression in individuals with mild-to-moderate AD.	 Change in cognition from Baseline to EOT visit as measured by: the change in the MoCA (Montreal Cognitive Assessment) score the change in the ADAS-cog₁₃ (Alzheimer's Disease Assessment Scale-cognitive subscale) score the change in the Clinical Dementia Rating Scale Sum of Boxes (CDR-SB) score the change in the Trail Making Test A (TMT A) score the change in the ADCS-ADL (Alzheimer's Disease Cooperative Study Activities of Daily Living Inventory) score the change in the Neuropsychiatric Inventory Score (NPI) the change in tests of Verbal Fluency (Semantic and Lexical) scores
To assess the effect of sargramostim treatment, as compared to placebo, on metabolic activity in different brain regions in individuals with mild-to-moderate AD.	Change from Baseline to EOT visit in FDG-PET assessment of metabolic activity, overall, as well in different brain regions, particularly in the medial temporal lobe in potential correlation with changes in MTA

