5.4.2 Additional Double Blind Treatment Study Procedures

In addition to the regularly scheduled collection of vital signs, conmed and AE review, labs, cognitive assessments, imaging and a physical/neurological exam will be completed at visits 12 and EOT. More detailed information can be found in a separate document, the Manual of Procedures.

Pharmacy orders will be submitted using the most recent weight documented for each participant, and coordinators will ensure the weight is within 3-weeks of the order submission. If a new weight is documented after order submission and by noon the day before the pharmacy dispenses, the coordinator will verify if the weight has changed by more than 3%. If the change is greater than this amount, a new pharmacy order will be submitted with the updated weight. If the change is less than this amount, the order will proceed with the original submission.

5.4.2.1 Double-Blind Treatment Labs – Visit 2 through 24

Prior to investigational product administration at weekly visits (Visit 2 through Visit 24), either at-home visits or research site visits, qualified medical staff will draw blood for safety labs and metabolic functioning (approximately 8 ml for CBC with differential and CMP) with two CBC with differential and one CMP per study week. Additionally, prior to administration of investigational product, on specific visits (Visit 6, 12, 18 and 24), there will be an additional blood draw for ADA testing (approximately 9 ml). If there are outstanding clinically significant lab values after CMP during week 24, additional CMP lab draw(s) may take place to resolve these clinically significant values, or the participant referred to their health care provider for clinical care follow-up, based upon the judgement of the PI.

An additional, weekly, safety blood draw (i.e. CBC with differential) will be completed. Depending on the participant's preference, the participant can either visit the CU -AMC site for the blood draw or the participant can travel to a local contracted lab site and have the safety draw (i.e. central contracted laboratory with phlebotomy services, as specified in Manual of Procedures). Lab results will be forwarded to study staff for review by the study physician. The EOT and FU Visits will comprise of a safety blood draw CBC w/differential and other specified labs per the schedule of events).

Additionally, a PT INR will also be drawn at Visit 24 in preparation for review prior to the EOT.

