5.5 Follow-up Visit

After the 24-week double-blind treatment period, all participants will be monitored during a 45-day follow-up period. At this visit, a physical/neurological exam will be performed, vital signs recorded, draw approximately 52 ml of blood for a CBC with differential, ADA analysis, and biomarker assays, and administer cognitive tests, including the MoCA, MMSE, ADAS-cog₁₃, the ADCS-ADL scale, Trail Making Test A, CDR, NPI, verbal fluency measures (lexical and semantic), and sleep-related measures (i.e. ISI, PSQI).

If the participant opted to engage in the Amyloid PET scan (either as entry criteria or optional), the PET will be performed using Vizamyl, and an MRI will be performed.

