5.6 End of Treatment / End of Study Definitions

End of Treatment is the date of the last Visit or scheduled procedure for a participant, as listed in the Schedule of Events (Section 2)

End of Study is the date of the last Visit or scheduled procedure for the last participant randomized, as listed in the Schedule of Events (Section 2)

Every attempt should be made to follow participants through their final visit of the double-blind treatment phase and follow-up visit. If a participant discontinues the study prematurely for any reason, all reasonable attempts will be made to complete an Early Termination Visit, which will consist of the events listed for the End of Treatment Visit.

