Common but non-life threatening side effects include:

- Fatigue or asthenia
- Malaise
- Rash
- Itching (pruritus)
- Vomiting
- Diarrhea
- Abdominal pain
- Sore throat (pharyngitis)
- Chills
- Bone pains
- Joint pains
- Weight loss or gain
- Elevations in kidney or liver enzymes
- Fluid retention (peripheral edema)
- Injection site irritation
- Insomnia
- Headaches
- Transient Fevers

Less common but potentially serious side effects include:

- Bleeding into the eye
- Allergic reactions
- Excessive increase in white blood cell count
- Fluid retention in the lung lining (pleura) and in the heart lining (pericardium)
- Shortness of breath
- Occasional transient heart rhythm changes (supraventricular tachycardia)
- Sweating, tachycardia, claustrophobia, or anxiety induced by the MRI procedure

Potential side effects of unknown frequency:

- Leukopenia (low white blood cell count)
- Neutropenia (low neutrophil count)

Adverse event of special interest (AESI) include:

An AESI is an AE (serious or non-serious) of scientific and medical concern specific to the program, for

which ongoing monitoring and immediate notification to the DSMB is required. Such events may require further investigation in order to characterize and understand them. Adverse events of special interest may be added or removed during a study by protocol amendment.

- ADA
- Acute hypersensitivity/anaphylaxis
- Leukopenia (low white blood cell count)
- Neutropenia (low neutrophil count)

Report of Unexpected Problems to the DSMB: The study coordinator will notify the PI or qualified sub-Investigator of any unexpected problems. The PI will contact the chair of the **DSMB** when unexpected problems arise that require immediate action.

Criteria for Action:

Specific triggers that will dictate when a specified action (such as reporting or stopping) is required. Any SAE or unexpected problem that meets the COMIRB criteria of reporting will be reported per COMIRB guidelines. Any serious AEs meeting the FDA reporting criteria, the FDA will also be notified according to their reporting guidelines.

Stopping rules:

Study: If treatment related serious AEs (SAEs) of Grade 3 or 4 occur in 20% of participants following sargramostim administration, the study will be stopped (Appendix F).

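### No routine metabolic panel is scheduled after the last dose, although the panel is a named component of the primary safety endpoint

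*Protocol*

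**What the plan says.** Section 4.5 lists what the primary safety endpoint is built from. Besides CBCs, MRI, vital signs and adverse events, it names "Comprehensive metabolic panels (CMPs), electrocardiograms (ECGs), serology testing for antidrug antibodies (ADAs), physical exams". Section 8.4.5.3 includes "Elevations in kidney or liver enzymes" in its list of common, non-life-threatening side effects to be monitored.

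On treatment, footnote k of the Schedule of Events (Section 2) and Section 5.4.2.1 set one CMP and two CBCs per week. Sections 5.4.1 and 5.4.2.1 place blood draws before that visit's injection.

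After treatment, three places leave the CMP out:
- Footnote k: "EOT and FU visits will not have a CMP, only one CBC draw will be collected for these visits".
- Synopsis, Safety Assessments: "At the End of Treatment Visit and follow-up visits, CBC with differential only".
- Section 5.5, follow-up: "approximately 52 ml of blood for a CBC with differential, ADA analysis, and biomarker assays".

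Section 5.6 provides for an "Early Termination Visit, which will consist of the events listed for the End of Treatment Visit", and Section 6.4.1 repeats the link to EOT. Footnote p keeps one laboratory test going after dosing: the "CBC w/ diff will be repeated approximately 2 days and 9 days after last participant dose at end of treatment or withdrawal from study".

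The one explicit route to a later CMP is in Section 5.4.2.1, and it is conditional: "outstanding clinically significant lab values after CMP during week 24, additional CMP lab draw(s) may take place to resolve these clinically significant values". Referral to the participant's own provider is the stated alternative, and the choice is left to the PI.

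**The concern.** The primary objective is long-term safety and tolerability, and chemistry is part of how the protocol says it will be judged. A value after the last dose does two things that on-treatment values cannot. It shows any effect of the final doses, and it shows whether an on-treatment change reverses once the drug is stopped. It supports a comparison between arms only if it is taken from everyone on the same schedule.

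The plan accepts this reasoning for blood counts, which are repeated at about 2 and 9 days after dosing as well as at EOT and follow-up. It does not apply it to chemistry, and it gives no reason for the difference.

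The same gap reaches people who stop early. Section 8.4.5.3 lets the PI or sub-investigator discontinue a participant whose value on any trial measure exceeds twice the upper limit of normal, which can include a liver or kidney value. The visit that then records the end-of-treatment state has no scheduled repeat of that value.

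**Working it through.** The protocol states no figure for this gap, so there is none to reproduce. The check compares the schedule with the text and counts visit days.

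**1. Primary-endpoint components at EOT** (Section 4.5 against the Schedule of Events)

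| Component | Scheduled at EOT? |
|---|---|
| CBC with differential | yes, plus about 2 and 9 days after the last dose |
| CMP | **no** |
| ECG | yes |
| Anti-drug antibodies | yes |
| Physical exam | yes |
| MRI | yes |
| Vital signs | yes |
| Adverse events | yes |

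The CMP is the only component not repeated.

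**2. Day count.** Inputs: weekly visits with a window of ±3 days, EOT 2 to 10 days after the last injection, follow-up ±7 days (Section 2); 168 treatment days (Section 5.4); 45-day follow-up (Section 5.5). Assumptions: baseline is day 1, dosing is uninterrupted, and the 45 days run from the last dose.

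- Week *n* visit = 1 + 7(*n* − 1). Week 24 = 1 + 7 × 23 = day 162; with ±3, days 159 to 165.
- Last dose = day 168. Because blood is drawn before that day's injection, doses with no later scheduled CMP = 168 − draw day + 1. This gives 168 − 162 + 1 = 7 nominally, 168 − 165 + 1 = 4 at the late edge and 168 − 159 + 1 = 10 at the early edge.
- EOT = 168 + 2 to 168 + 10 = days 170 to 178, with no CMP.
- Follow-up = 168 + 45 = day 213; with ±7, days 206 to 220, again with no CMP.
- Week 24 panel to follow-up = 213 − 162 = 51 days; range 206 − 165 = 41 to 220 − 159 = 61.

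**3. Scheduled panels per completer.** Baseline plus weeks 2 to 24 = 1 + 23 = 24, of which none follows the last dose. Adding a CMP at EOT and follow-up gives 24 + 2 = 26, of which two follow the last dose. An early stopper goes from none to one at the Early Termination Visit, or two if follow-up is also attended.

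**4. Is the week 24 panel itself secure?** Section 5.4.2.1 has a weekly draw, at home or at the site, of about 8 mL for CBC and CMP. Sections 5.7.1 and 5.7.2 describe the home-visit draw as CBC with differential only, about 4 mL in Section 5.7.1. Week 24 is among the home visits. If the home-visit text governed for a participant using that option throughout, panels would fall only at baseline and weeks 6, 12 and 18. Week 18 = 1 + 7 × 17 = day 120, so the last panel would precede the last dose by 168 − 120 = 48 days (45 to 51).

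**The case against.** The best defence is that this is a consistent choice and not a slip. Footnote k, the Synopsis and Section 5.5 all agree. The component is measured often on treatment, with about 24 panels per completer, and Section 4.5 does not itself demand a post-dose value. Post-dose sampling follows what Sections 7.4 and 8.4.5.2 call the greatest safety concern, excessive leukocytosis. A clinically significant week 24 value may be redrawn under Section 5.4.2.1. Other text also leaves a CMP open: Section 8.2 allows blood draws at unscheduled visits, Section 8.4.5 requires follow-up of adverse events that caused discontinuation, and Section 8.4.5.3 follows such events to recovery or stabilization.

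Much of this stands, and it rules out several stronger readings that a reader might infer:

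- *That the plan forbids any post-dose CMP, or that chemistry is never measured after the last dose.* Section 5.4.2.1 expressly allows further panels. What is missing is a routine one.
- *That early discontinuers have the thinnest chemistry data.* This is not shown. Under the weekly schedule they have panels until they stop, so the last one normally lies within about a week of their last dose, as it does for completers. Fewer panels in total reflect shorter exposure.
- *That footnote k's single CBC contradicts footnote p.* It does not. The EOT safety-draw cell carries footnote p, and the Synopsis states both rules side by side. The single draw contrasts with the twice-weekly draws on treatment.

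The defence does not close the gap. The Section 5.4.2.1 route is discretionary, has referral as an alternative, needs a value already judged significant at week 24, and does not expressly cover people who stop earlier. Adverse-event follow-up names no CMP and starts only once an event has been recognised. Neither yields comparable post-dose chemistry in both arms.

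**Conclusion.** The point holds as a weakness of design, not as an internal contradiction. No routine CMP is scheduled after the last dose at EOT, Early Termination or follow-up, while every other named primary-endpoint component is repeated at EOT. The Early Termination part is an inference from Sections 5.6 and 6.4.1, since footnote k does not name that visit, but it is a short and sound one.

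About 7 doses (4 to 10) have no later scheduled chemistry, and about 51 days (41 to 61) pass between the week 24 panel and follow-up without one. These figures rest on the day-count assumptions above and on the week 24 panel actually being drawn. For home-visit participants that depends on resolving the conflict between Section 5.7 on one side and Section 5.4.2.1 and footnote k on the other, which is a genuine contradiction.

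The consequence is limited. On-treatment chemistry is well covered if the weekly schedule applies, and abnormalities already recognised can be followed. What is not captured systematically is a new or delayed change after the last panel, and reversal off drug. In a trial whose primary objective is safety, and at this cost, the change should be made.

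**What to change.** Add a CMP to the existing EOT/Early Termination blood draw and to the existing follow-up draw. Amend footnote k, the Safety Assessments entry in the Synopsis and Section 5.5 to match, and name the Early Termination Visit in footnote k so that its content need not be inferred. The discretionary route in Section 5.4.2.1 can stay as it is.

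Separately, reconcile Sections 5.7.1 and 5.7.2 (home draw: CBC only) with footnote k and Section 5.4.2.1 (weekly CMP at home or at the site), so that it is clear whether home-visit participants have a week 24 panel.

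Cost: at most two extra assays per participant. With about 47 randomised (Synopsis), the ceiling is 2 × 47 = 94, reached only if everyone attends both visits. Blood is already drawn at both visits, so no new visit or needle stick is needed. The extra volume is a few mL each time; the two draw volumes in the text suggest about 8 − 4 = 4 mL. No dosing or stopping rule changes.

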4.1 Introductory Statement and General Investigational Plan

This trial protocol is designed to evaluate primarily whether the long-term use of sargramostim (recombinant human GM-CSF), administered five days per week for six consecutive months (24 weeks), will be tolerated by and safe for use in participants with mild-to-moderate AD, secondarily whether sargramostim can slow, halt, or reverse cognitive decline, and exploratory whether sargramostim can slow, halt, or reverse decline in activities of daily living, reverse or improve several biomarkers associated with AD, as evaluated by multimodal neuroimaging techniques and blood and cerebrospinal fluid analyses. This trial extends the safety results from recently completed Phase 2 double-blind, placebocontrolled clinical trial in mild-to-moderate AD participants (NCT01409915, COMIRB#12-1273), using sargramostim that was administered five days per week for three consecutive weeks and in which there were no incidence of drug-related serious adverse events (SAEs). This concluded in December 2019, and although the trial only treated a small number of participants for a very short treatment phase and was not powered to adequately evaluate efficacy measures, an interim analysis has hinted at potential improvements in some secondary and exploratory efficacy measures. Thus, this 6-month trial protocol aims to evaluate sargramostim treatment in participants with mild-to-moderate AD over an extended period of time and determine whether sargramostim can indeed safely ameliorate cognitive decline and reverse pathological biomarkers of AD, in a similar fashion to our preclinical studies showing GM-CSF's effects in transgenic animal models of AD (1, attached as Appendix B).

